Study Description	This is a single-site, parallel-arm double-blind randomized controlled pilot trial (N=12) of 0.5mg/kg oral ketamine vs. 0.5mg/kg intramuscular ketamine, each administered as a single dose, in combination with 4 sessions of Meaning and Purpose therapy (MaP), for adults diagnosed with stage 3 or 4 gastrointestinal (GI) cancers (i.e., primary pancreatic, colorectal, hepatocellular, biliary, and gastro-esophageal cancers) who have moderate-to-severe demoralization. The combination of ketamine and Meaning and Purpose therapy will be referred to as K-MaP.			
MaP is a brief, existential behavioral intervention. It is a form of talk therapy designed to help patients cope with demoralization through review of the patient's value and worth, their key relationships, and sources of fulfillment and meaning in life [1]. Participants will have sessions of MaP before drug administration, and 2 sessions after administration. The expected study duration from enrollment to stu completion is up to 63 days for each participant.				
	Demoralization is a clinically significant and measurable form of existential distress characterized by poor coping and a sense of helplessness, hopelessness, and a loss of meaning and purpose in life [2, 3]. Demoralization will be measured by Demoralization Scale-II (DS-II), a validated measure [4]. The scale includes 16 items, the total score range is 0-32, and a score of 10 or higher indicates moderate-to-severe demoralization [4, 5]. DS-II will be assessed at baseline, after 2 sessions of MaP but before ketamine, and then 1, 2, and 5 weeks after ketamine. A change in the DS-II of at least 2 points has been considered clinically meaningful in palliative care patients and will be used as a minimum point reduction indicative of efficacy [4].			
Phase of Study	Pilot			
Investigational Products Ketamine				
Study population	Adult stage 3 and 4 GI cancer patients with moderate to severe demoralization.			
Primary Objective	To assess the feasibility of Meaning and Purpose therapy combined with ketamine (K-MaP) in demoralized patients.			

Pilot Study - Ketamine Page 3 of 55

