the study team will read the questions to the potential participant, and the potential participant's answers will be recorded by the study team. If the score is ≥10/32, the study team will talk to the participant about joining the study. The data from the phone screen will only be used for screening and will not be used as research results. The second DS-II measurement will be given to the participant in person after they have signed the informed consent form on the day of enrollment (i.e. baseline, between Day -28 and -7). The DS-II questions will be administered to the patient either on paper or electronically with a tablet (using REDCap). Following best practices with patient-reported outcomes [73], participants will fill out the second DS-II without clinician or study staff involvement. In the event that a participant has a question about how to fill out the questionnaire, study staff will be trained only to read the instructions printed at the top of the measure or to assist the participant with reading a particular item, but staff will say nothing beyond reading the wording on the instrument itself. The DS-II will be scored by summing the responses to all 16 items to generate a total score. Participants must score a 10 or higher in order to be eligible for the study.

If the participant meets all of the eligibility criteria, they will be randomized 1:1 on Day 0 to one of two cohorts (0.5 mg/kg of ketamine PO or 0.5 mg/kg of ketamine IM). The study is double-blinded, meaning neither the study participants nor the study investigators will know which dose of ketamine each participant is receiving. Participants randomized to receive ketamine 0.5 mg/kg PO will receive an equivalent quantity of normal saline (placebo) via an intramuscular injection after ingesting oral ketamine, and those who are randomized to receive ketamine 0.5 mg/kg IM will receive their IM injection after ingesting an equivalent quantity of normal saline (placebo) orally. Orally administered ketamine and normal saline (placebo) will be mixed in cranberry juice immediately prior to being administered to the patient.

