3.3 Eligibility Criteria

3.3.1 Inclusion Criteria

In order to be eligible to participate in this study, an individual must meet all of the following criteria:

- 1. Must have a diagnosis of a stage 3 or 4 primary GI (i.e., pancreatic, colorectal, hepatocellular, biliary, and gastro-esophageal) cancer.
- 2. Must be willing to sign the informed consent form (ICF) and follow the study procedures as outlined in the ICF for the duration of the study.
- 3. Must be 18 years or older.
- 4. Must speak English and/or Spanish.
- 5. Must have a Palliative Performance Score (PPS v. 2.0) greater than or equal to 40%. *Note: See Appendix 1.*
- 6. Must be able to swallow liquid oral medication.

Pilot Study - Ketamine Page 18 of 55

- 7. Must self-report moderate-to-severe demoralization (DS-II≥10 per Demoralization Scale-II) that is stable.
 - Note: Stable is defined as DS-II ≥10/32 two times ≥7 days apart.
- 8. Must discontinue the following medications and refrain from taking them for the duration of study participation (participants who require these medications will be taken off study):
 - a) Lamotrigine
 - b) Clozapine
 - c) PRN (as-needed) anxiolytics
 Note: Benzodiazepine use may be allowed if used in a regular, scheduled way. Consultation
 with the Principal Investigator is recommended.
 - d) Dopamine agonists
 - e) Lithium
- 9. Female-born participants of child-bearing potential with male-born partners must use highly effective contraception for at least 1 month prior to ketamine administration (on day 0) and agree to use such a method for an additional 2 months after ketamine administration.
- 10. Male-born participants with female-born partners of child-bearing potential must use highly effective contraception for at least 1 month prior to ketamine administration and agree to use such a method for an additional 2 months after ketamine administration.

Note: Highly effective contraception include:

- Intrauterine device (IUD)
- Intrauterine hormone-releasing system (IUS)
- Non-oral hormonal methods, including injected, intravaginal, implanted, transdermal
- Oral hormones plus a barrier contraception (condom, diaphragm, or spermicide)
- Double barrier method (at least two of the following: condom, diaphragm, and spermicide)
- Vasectomy
- Abstinence from penile-vaginal intercourse*

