Secondary Objective #2: To assess the magnitude and durability of improvement from randomization in psychosocial distress associated with K-MaP, we will measure mean trends in patient-reported outcomes (DS-II, PHQ9, GAD7, FACIT-PAL-14 scores) in each study arm from baseline visit (Day -28 to -7) to post-ketamine (on Days 7, 14, and 35). In addition, we will calculate the proportion of participants per arm who no longer meet criteria for moderate-to-severe demoralization (i.e., DS-II > 10) post-ketamine. We will also measure mean trends in clinician-rated outcomes (CGI-S, DI, and GRID-HAMD-6 scores) per arm as above. ANCOVA models of follow-up endpoints as a function of study arm, adjusted for endpoints at baseline and randomization, will be conducted [110]. ANCOVA results will be presented graphically via mean trends per arm overlaid on individual trends, and via the mean (95% CI) difference between arms at Day 35. Cohen's d will be calculated at each follow-up time to estimate effect sizes. Any missing data will be estimated through the use of single imputation with baseline observations carried forward.

Secondary Objective #3: We will evaluate BPI-SF scores analogously to DS-II scores.

Secondary Objective #4: We will evaluate opioid analgesia use analogously to DS-II scores.

Secondary Objective #5: We will be using pair t-tests to measure mean changes in MAIA-2 scores in each study arm from prior to ketamine administration (on Day 0) to post-ketamine (on Day 7).

Secondary Objective #6: To assess how participants' subjective experiences with ketamine may be related to clinical outcomes, subjective reports of each participant's ketamine experience (videorecorded from Day 0) will be transcribed, inductively coded, and qualitatively analyzed to identify phenomenological content. In addition, participant MEQ and CEQ scores, which provide summary measures of the intensity of ketamine's acute effects, will be evaluated for potential correlation with trends in DS-II, BPI-SF, and opioid use.

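### The DS-II proportion in 9.2.3 counts any post-ketamine score across the entry cut-off, with no Day 0 reference, no named visit and no use of the protocol's own 2-point minimum, so it does not measure improvement from randomization or its durability.

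*Combined protocol and SAP*

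**What the plan says.** Section 9.2.3, Secondary Objective #2, sets out to describe how large the improvement in psychosocial distress since randomization is and how long it lasts. After the mean trends it adds that "we will calculate the proportion of participants per arm who no longer meet criteria for moderate-to-severe demoralization", with the criterion given in brackets as "i.e., DS-II > 10) post-ketamine". Nothing else defines the proportion. The three follow-up visits, "post-ketamine (on Days 7, 14, and 35", appear in the sentence before, where they belong to the mean trends.

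Three other places bear on it:

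- **Entry.** Section 3.3.1, criterion 7, requires stable demoralization: "Stable is defined as DS-II ≥10/32 two times ≥7 days apart". Section 3.1 adds: "Participants must score a 10 or higher in order to be eligible for the study".
- **Minimum change.** The Study Description in the abstract says that a DS-II change of at least 2 points "will be used as a minimum point reduction indicative of efficacy". Section 9.2.3 does not mention this figure.
- **Day 0 score.** The study calendar (6.1, note 5) schedules DS-II at Visit 4 before ketamine, after two MaP sessions, so a reference score at randomization exists for this purpose.

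**The concern.** The proportion records on which side of the entry cut-off a participant sits at some time after ketamine. It does not record movement since randomization. Three gaps follow from the text alone:

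1. **No Day 0 reference.** A participant who fell below 10 during the two MaP sessions before ketamine, or by chance at Visit 4, can be counted after ketamine without any further change.
2. **No visit rule.** One visit, each visit or any visit would all fit the sentence. They give different numbers, and the choice could be made after the data are seen. Nothing asks for the lower score to be held, although durability is part of the objective.
3. **The 2-point minimum is not applied.** A score of 10 on Day 0 and 9 once later counts, although that 1-point change is smaller than the protocol's own minimum.

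Every participant receives ketamine, so no arm shows how often scores cross the cut-off without it. With six per arm, one participant moves an arm's proportion by 1/6, or 17 percentage points.

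**Working it through.** **Figure in the plan.** The documents give no expected proportion, error rate, SD or reliability for DS-II, so there is no stated figure to reproduce. The sizes below rest on assumptions.

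**Inputs from the documents.** DS-II is an integer from 0 to 32. Entry needs two scores of 10 or more. Later scores are at Visit 4 (Day 0), Visit 6 (Day 7), Visit 8 (Day 14) and Visit 9 (Day 35). There are six participants per arm.

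**Assumptions.** In referred patients the true score is N(mean 12, SD 4). Each reading adds independent normal error with SD 2 and is rounded. There is no effect of ketamine, MaP or time. The range covers true mean 8 to 14, between-person SD 4 to 5 and within-person SD 1.5 to 3. Crossing is taken as a score below 10, matching entry. The figures therefore do not depend on the "i.e., DS-II > 10) post-ketamine" wording, under which a participant who stays at exactly 10 would be counted with no change at all.

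**Step 1: one participant, closed form.** P(score below 10) = P(Z < (9.5 − true score)/2).

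- True score 11: P(Z < −0.75) = 0.227.
- True score 14: P(Z < −2.25) = 0.012.

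Noise matters mainly for participants close to the cut-off.

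**Step 2: the enrolled group.** Simulation of 2 million people, keeping those with both entry scores at 10 or more:

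| Quantity, no true change | Central | Range |
|---|---|---|
| Already below 10 on Day 0, of all enrolled | about 8% | – |
| Below 10 at one given visit, of those at 10 or more on Day 0 | 5.8% | 2.3–18.3% |
| Below 10 at any of three visits, same group | 13.6% | 5.5–38.8% |
| Below 10 and at least 2 points down, one visit | 5.2% | – |
| The same at both Day 14 and Day 35 | 1.2% | 0.4–5.6% |

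**Step 3: an arm of six, all at 10 or more on Day 0.**

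- One named visit: expected count 6 × 0.058 = 0.35; P(at least one) = 1 − (1 − 0.058)^6 = 0.30.
- Any of three visits: expected count 6 × 0.136 = 0.82; P(at least one) = 1 − (1 − 0.136)^6 = 0.58.

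**Step 4: a second set of assumptions.** Mean/SD in screened patients 8/5, 10/6, 14/6 and 16/5, with test-retest reliability 0.7 to 0.9, counting all enrolled. Scores below 10 occur in 2.1–21.1% at one visit and 4.7–41.7% at any of three. In the case 10/6 with reliability 0.8, 12.1% are below 10 on Day 0. The level moves with the assumptions. In both sets the any-visit rate is roughly double the one-visit rate.

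**Step 5: what a confirmed rule would cost.** With a true 2-point fall after ketamine in the central case, 17.6% are credited at a single visit with the 2-point minimum, but only 7.6% if this must hold at both Day 14 and Day 35. Under the confirmed rule six participants would show nobody with probability (1 − 0.076)^6 = 0.62.

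**The case against.** The strongest reply is that this is a summary of status, not a responder analysis. The plan attaches no test, expected rate or success threshold to it, and a status measure needs no minimum change. The same paragraph covers change and durability by other means: mean trends, ANCOVA adjusted for the baseline and randomization scores, individual trends plotted over arm means, the Day 35 difference with its interval, and Cohen's d at each follow-up. Section 9.1.1 rules out formal efficacy tests and bases its next-step criteria on the mean DS-II improvement. Most of this stands, and it limits the consequence. It does not remove the mismatch: the proportion is listed under an objective about improvement since randomization, and it is neither tied to Day 0 nor given a visit.

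A reader might infer three stronger things that the documents do not support:

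- **That noise gives each arm a 58% chance of a false responder.** This needs an any-visit rule, which the plan does not state. Reading the proportion visit by visit is equally natural and gives 30% in the central case.
- **That the missing 2-point minimum is the main source of false crossings.** Adding it alone only moves 5.8% to 5.2%. The reason to add it is consistency with the abstract.
- **That a confirmed two-visit rule should replace the proportion.** Entry on two scores does not logically require exit on two, and Step 5 shows how few true 2-point improvers such a rule credits.

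Noise also acts on both randomized arms alike in expectation. A chance imbalance in starting scores affects any summary with six per arm.

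**Conclusion.** The point holds as a gap in definition. The proportion in 9.2.3 counts any post-ketamine crossing of the entry cut-off. It has no reference to Day 0, no named visit and no use of the 2-point reduction, so it does not describe improvement from randomization or its durability. These facts need no assumption.

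The size does. With no true change, about 6% of those at 10 or more on Day 0 cross at a given visit (2% to 18%) and about 14% at any of three. About 8% of enrolled participants are already below 10 on Day 0. All of this rests on assumed means and SDs, and on no effect of the two MaP sessions before ketamine.

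The change is worth making because it is cheap and fits the stated objective. The trial's feasibility conclusions and the next-step criteria in 9.1.1 do not depend on it. The harm is confined to reading an arm's proportion as benefit.

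**What to change.** Amend the sentence in 9.2.3, before unblinded data are reviewed, to say:

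- The denominator is participants with DS-II of 10 or more at Visit 4 (Day 0), by arm.
- At each of Days 7, 14 and 35, report as a count out of that denominator those with DS-II below 10 and at least 2 points below their Visit 4 score.
- As the durability summary, also report the count meeting this at both Day 14 and Day 35. This is added to the by-visit counts and does not replace them.
- Report separately how many were already below 10 at Visit 4.
- Keep the plan's baseline-carried-forward rule, or state explicitly what replaces it for this proportion. Every Visit 1 score is 10 or more by eligibility, so carrying it forward classes a missed follow-up visit as not below 10.

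Writing the criterion as below 10 also brings it into line with the entry rule.

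**Cost.** A few lines of text, using scores already scheduled. The denominator may fall below six in an arm, and the proportions will be somewhat lower than under the present wording.

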3.1 Characteristics

This is a parallel-arm, double-blind, randomized controlled pilot trial (N=12) of two different dose levels of ketamine administered as a single dose, in combination with 4 sessions of Meaning and Purpose therapy (MaP) for stage 3 and 4 GI cancer patients (including those with primary pancreatic, gastroesophageal, hepatocellular, biliary, and colorectal malignancies) experiencing moderate-to-severe demoralization.

Demoralization is a clinically significant and measurable form of existential distress characterized by poor coping and a sense of helplessness, hopelessness, and a loss of meaning and purpose in life [2, 3]. Demoralization will be measured by Demoralization Scale-II (DS-II), a validated measure [4]. The scale includes 16 items, and a total score of 10 or higher indicates moderate-to-severe demoralization.

Participants will be administered 2 sessions of MaP before drug administration, and 2 sessions after drug administration. The combination of ketamine and Meaning and Purpose therapy will be referred to as K-MaP.

Adult GI oncology patients at HDFCCC and other Bay Area medical centers will be referred by their clinical teams. Referred patients must demonstrate clinically significant and stable demoralization as measured by DS-II ≥10/32 two times ≥7 days apart (both during screening) to be eligible for the study. The first measurement of the DS-II scale will occur over the phone. After a verbal waiver of consent,

Pilot Study - Ketamine Page 17 of 55

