9.1 Sample Size Considerations

9.1.1 Sample Size and Power Estimate

No formal power analysis was conducted, and no formal tests of efficacy will be conducted. This N=12 pilot study has a sample size sufficient for assessing the feasibility and preliminary safety of a novel behavioral-pharmaceutical intervention, at two different dose levels and routes of administration of the study drug.

If the 0.5mg/kg PO dose of ketamine is well-tolerated (i.e., zero treatment-related SAEs) and demonstrates mean clinical improvement in demoralization assessed by DS-II that endures beyond 7 days post-drug, then this would suggest a fully powered study is warranted using the 0.5mg/kg PO dose.

If the 0.5mg/kg IM dose of ketamine is well-tolerated (i.e., zero treatment-related SAEs) and demonstrates mean clinical improvement in demoralization assessed by DS-II that endures beyond 7 days post-drug, then this would suggest a fully powered study is warranted using the 0.5mg/kg IM dose.

If the either dose is well-tolerated and fails to demonstrate mean clinical improvement in demoralization assessed by DS-II that endures beyond 7 days post-drug, then this would suggest that the dose is an appropriate control for other psychoactive investigational drugs whose clinical effects are expected to have greater durability.

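### Section 9.2.3 codes moderate-to-severe demoralization as DS-II > 10, while the rest of the protocol uses 10 or more, so an unchanged score of 10 counts as no longer demoralized

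*Combined protocol and SAP*

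**What the plan says.** The cutoff for moderate-to-severe demoralization is stated in several places.

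- Abstract, Study Description: "a score of 10 or higher indicates moderate-to-severe demoralization".
- Section 3.1, defining the scale: "a total score of 10 or higher indicates moderate-to-severe demoralization".
- Section 3.1, on the second (in-person) screening measurement: "Participants must score a 10 or higher in order to be eligible for the study".
- Section 3.3.1, inclusion criterion 7: "Stable is defined as DS-II ≥10/32 two times ≥7 days apart".

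Section 9.2.3, Secondary Objective #2, then defines a responder-type summary by arm, the proportion "who no longer meet criteria for moderate-to-severe demoralization (i.e., DS-II > 10) post-ketamine". The same paragraph gives the missing-data rule: "Any missing data will be estimated through the use of single imputation with baseline observations carried forward".

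No section says that a different cutoff is meant after ketamine.

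**The concern.** Section 9.2.3 names the same clinical category that governs entry but attaches a different inequality to it. A participant can therefore be inside the category at enrollment and outside it at follow-up with no change in score. The abstract treats a drop of 2 DS-II points as the smallest that indicates efficacy; here a drop of 0 would be enough.

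The missing-data rule adds a second route. A participant who enters at 10 and has no follow-up score is imputed at 10, and so is also counted as no longer demoralized. Carrying the baseline forward would normally count such a person as not improved.

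On the natural reading, where the parenthesis restates the criterion, the literal rule can only raise the reported proportion. With six participants per arm, one person is enough to change the figure visibly.

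**Working it through.** **Inputs from the documents.** DS-II is the sum of 16 items with total range 0 to 32 (Abstract; Sections 3.1 and 6). There are 6 participants per arm and 12 in total (Abstract, Sample Size). Entry requires a score of 10 or more twice, at least 7 days apart (Sections 3.1 and 3.3.1). The plan gives no calculation that depends on the post-ketamine cutoff, so there is no planned figure to reproduce.

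**Step 1: where the two rules differ.** Applying both rules to every whole-number score from 0 to 32, they disagree only at 10.

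| DS-II score | Eligible (≥ 10) | No longer meets, criterion > 10 | No longer meets, criterion ≥ 10 |
|---|---|---|---|
| 9 | no | yes | yes |
| 10 | yes | **yes** | **no** |
| 11 | yes | no | no |

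**Step 2: effect per participant.** One affected participant moves an arm by 1/6 = 16.7 percentage points, and two move it by 2/6 = 33.3 points.

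**Step 3: expected effect.** The excess in the proportion equals d, the probability that an eligible participant scores exactly 10 at follow-up:

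d = P(score ≤ 10) − P(score < 10)

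The documents give no DS-II mean, SD or within-person correlation, so d was simulated under assumptions:

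- Each measurement is a true score plus independent error, rounded and limited to 0–32.
- The mean before selection is 8, 10, 12 or 15, the SD is 5 or 6, and the ICC is 0.6 to 0.9.
- Eligibility requires 10 or more at both the phone screen and Visit 1.
- Follow-up uses the same true score with new error and no treatment effect.

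| Assumed mean before selection | Excess d (percentage points) |
|---|---|
| 8 | 6.9–9.0 |
| 10 | 5.9–7.4 |
| 12 | 4.6–5.9 |
| 15 | 3.0–3.6 |

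Overall d runs from 0.030 to 0.090. Per arm that is 6 × 0.030 = 0.18 to 6 × 0.090 = 0.54 participants.

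For example, with mean 10, SD 6 and ICC 0.7, the proportion is 21.8% under > 10 and 15.9% under ≥ 10, a difference of 5.9 points.

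**Step 4: chance that it matters at a given visit.** The probability that at least one participant scores exactly 10 is 1 − (1 − d)^n.

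- One arm, n = 6: 1 − 0.970^6 = 0.17 to 1 − 0.910^6 = 0.43.
- Whole trial, n = 12: 1 − 0.970^12 = 0.31 to 1 − 0.910^12 = 0.68.

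**Step 5: sensitivity to a treatment effect.** On the same grid, an assumed mean fall gives these values of d:

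- 2 points: 5.2–13.4%
- 4 points: 6.7–11.6%
- 6 points: 6.1–9.4%

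The no-effect range is therefore not an upper bound. At d = 0.134 the whole-trial chance is 1 − 0.866^12 = 0.82.

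These figures count everyone at 10. Some will have come down from a higher score; they have improved but still meet the protocol's criterion.

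**The case against.** The strongest reply is that the operative words in Section 9.2.3 refer to an established category, and the parenthesis merely restates it with a slipped symbol. An analyst who follows the defined term would use 10 or more and no error would reach the results. That is a fair account of how the text probably arose. But the parenthesis is the only explicit coding rule for this proportion, and an analyst who programs it as printed gets the wrong answer.

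The sign might also have been lost when the PDF was read. This cannot be fully excluded, but ≥ survives in the symbolic DS-II cutoffs in Sections 3.1 and 3.3.1.

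The parenthesis could instead be taken to describe those who no longer meet the criterion, which would reverse the direction. That reading is unnatural, since it would call high scorers recovered, and it would need correcting too.

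Two limits stand. First, the consequence is small: Section 9.1.1 says that "no formal tests of efficacy will be conducted", both arms share the rule, and in the worked example 15.9 of the 21.8 points remain after correction. Second, the simulated sizes depend on assumed distributions and, in the main range, on no treatment effect.

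**Conclusion.** The threshold in Section 9.2.3 is wrong as written: it contradicts the definition used in the Abstract and in Sections 3.1 and 3.3.1, and nothing in the documents reconciles them. What rests on the documents alone is that one score value is misclassified, that it is the lowest score allowing entry, and that each participant with that score moves an arm by 16.7 points. The expected excess of 3.0 to 9.0 points holds only under the stated assumptions with no treatment effect, and could be larger with a modest one.

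The issue is minor. It affects one descriptive secondary proportion. Mean trends, ANCOVA estimates and Cohen's d use the scores themselves and do not change. The feasibility criteria in Section 9.2.2 and the progression rules in Section 9.1.1 do not use this proportion.

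**What to change.** In Section 9.2.3, Secondary Objective #2, replace > 10 with ≥ 10, so that a participant no longer meets the criterion when the post-ketamine DS-II is 9 or less.

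The missing-data rule then needs no change for this summary. Every entrant has a Visit 1 score of at least 10, so carrying that baseline forward counts an unobserved participant as still meeting the criterion.

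The sentence on the proportion says only that it is taken after ketamine; Days 7, 14 and 35 are named in the sentence before it. Repeating those days would be a useful clarification while the text is open, but the correction does not depend on it.

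The cost is one symbol, and the reported proportion may come out slightly lower. Making the change before the data are analysed avoids choosing the cutoff after the scores are known.
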